Safety monitoring will occur during the initial baseline visit as well as throughout the participant's duration in the study, including a 1-week follow-up contact after study termination. As noted below, the baseline assessment conducted during the first visit will include a brief physical exam (including vital signs) and a thorough medical and psychiatric history, including a review of past medical history, concomitant medications, inclusion/exclusion criteria, and potential contraindications. Safety monitoring will include active and passive surveillance procedures using pre-existing safety monitoring guidelines. Participants will be assessed actively at each laboratory visit by study personnel using the side effects/adverse events checklist. Each participant will be read each side effect/adverse event from the checklist and instructed to selfreport as yes (go) or no (no go). If a participant experiences any of the side effects/adverse events from the checklist provided at the baseline visit, study personnel will then contact the study physician ([name]) for consultation and guidance. The side effects/adverse events will be triaged as mild, moderate or severe, and a determination will be made by the study physician as to whether the side effect/adverse event is due to the investigational test article or some other circumstance (e.g. food poisoning). If the reaction or event is determined to be due to the investigational test article and graded moderate to severe by the study physician, the participant will then be instructed to stop participation and advised to seek medical care by their primary physician or hospital. (Refer to stopping criteria below). In the event that emergency care needs to be provided the participant is instructed to immediately call 911 or seek care at a medical health facility (e.g. hospital). The study physician ([name]) would also be contacted for guidance as well. Any serious adverse reaction or event will be followed until full resolution. All adverse reactions and events will be reported to the UF IRB within 24-48-hrs and documented in the participant's file (redcap).

Stopping criteria:

- 1. The PI/physician decides that the participant should be withdrawn for **safety reasons** (presence of active lesions in the oral cavity/sublingual region or suffering side effects or adverse events associated with the use of the investigational product).
 - a. List of side effects and adverse reactions are listed below*

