- 2. Participant is unwilling to continue in the study.
- 3. Lack of compliance with protocol.
- 4. Investigator or study sponsor stops the study for any reason.
- 5. Participant becomes pregnant.
- 6. Participant is enrolled in error or lost to follow-up (lost to follow-up will be defined as a subject failing to attend planned study visits or failure to respond to contacts by study personnel after documented 2 attempts).

*Potential Side Effects and/or Adverse Events (AEs):

- Feelings of anxiety (nervousness, restlessness or being tense, feelings of danger, panic, or dread), paranoia, or negative mood (depression or suicidal thoughts), or paranoia.
- 2. Poor quality of sleep (persistent insomnia).
- 3. Feelings of extreme fatigue, sleepiness or drowsiness.
- 4. Feelings of nausea (upset stomach, vomiting or gastro-intestinal (GI) distress (e.g. diarrhea).
- 5. Change in or loss of appetite.
- 6. Feelings of light-headedness or dizziness.
- 7. Visual disturbances such as blurry/double vision or dilated pupils.
- 8. Hypotension, hypertension, tachycardia, heart palpitations, syncope or dyspnea.
- 9. Development of a skin rash with redness and itching.
- 10. Loss of muscle coordination (clumsiness)
- 11. Muscle spasms

Visit 1 (Consenting, screening, randomization and test product distribution, Day 1)

Participants will be consented. Consenting will be performed by one of the co-investigators in a private room. The following procedures will be performed: urine sample for pregnancy (females) and toxicology screen (presence of cannabinoids), a brief physical exam (including vital signs: measurements for height, weight, pulse, blood pressure and body temperature), obtaining a thorough medical and psychiatric history, including a review of past medical history, concomitant medications, inclusion/exclusion criteria and potential contraindications, assessment of the oral cavity and sublingual area to rule out any active lesions or abnormalities (bleeding, sores, ulcers, abscesses, etc.). If any lesions are found to be present, the research assistant will document the findings and follow up with a consultation phone call with the study physician to determine next steps. The study participant may choose to be excluded from participation or wait until the condition fully resolves. If the participant continues with the study protocol, follow up oral assessments will be repeated at visits 2 through 6.

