Results of urine screening for pregnancy and toxicology (presence of cannabinoids) will be available and assessed during the first visit. If the urine test (pregnancy or cannabinoids) comes back positive, the participant will be excluded from the study. The participant will complete several psychological questionnaires (FPQ-9, PCS, PASS-20, PSQI, & LEFS), followed by tests for muscle soreness and quantitative sensory testing (QST). Each participant will be provided a detailed safety monitoring checklist of side effects and/or adverse reactions that they may potentially experience from ingesting the investigational product. Participants will then be instructed on how to perform their own passive surveillance for identifying these side effects/adverse events and what to do if they experience any of them between study visits while they are ingesting the investigational test article (Days 1 through 10). Participants will be instructed to maintain current activity levels and not to initiate a resistance-training or weightloss program for the duration of the study. Participants will then be randomly assigned to an experimental group and instructed on how to ingest the investigational test article (or placebo) and dosing procedures, which will be dispensed in a quantity to last for the next 15 days. Each participant will be provided a daily log chart to record their daily CBD doses for compliance and monitoring purposes. A pre-exercise visit will be scheduled. Each subject will receive \$10 for completion of the test session.

During the passive surveillance period (Days 1 through 10) participants will be instructed to contact the PI ([name]) if they experience any of the side effects/adverse events from the checklist provided at the baseline visit. [name]/[name] will then contact the study physician ([name]) for consultation. The side effects/adverse reactions will be triaged as mild, moderate or severe, and a determination will be made as to whether the side effect/adverse reaction is due to the investigational product or some other circumstance (e.g. food poisoning). If the event is determined to be due to the investigational test article and graded moderate to severe by the study physician, the participant will then be instructed to stop participation and seek medical care by their primary physician or hospital. Any participant that reports a serious adverse event will be followed to full resolution.

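### Mouth lesions are a ground for withdrawal, but the printed side-effect list has no mouth item, so participants may have no prompt to report one between Visit 1 and Visit 2 (Day 11)

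*Combined protocol and SAP*

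**What the plan says.** All references are to the Combined protocol and SAP, Research Plan.

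- **Stopping criteria, item 1.** The PI/physician may withdraw a participant for safety reasons. Two are named: "presence of active lesions in the oral cavity/sublingual region", or side effects or adverse events associated with the product. A sub-item points to a list below.
- **The list of side effects and adverse events.** It has 11 items: anxiety or mood, sleep, fatigue, nausea/GI, appetite, dizziness, vision, cardiovascular signs or dyspnea, skin, coordination and muscle spasms. The closest to a mucosal reaction is item 9, "Development of a skin rash with redness and itching", which concerns skin only.
- **Visit 1 (Day 1), oral examination.** Procedures include "assessment of the oral cavity and sublingual area to rule out any active lesions or abnormalities". After instructions on what to do if a lesion is found, the text adds: "If the participant continues with the study protocol, follow up oral assessments will be repeated at visits 2 through 6".
- **Visit 1, self-surveillance.** "Each participant will be provided a detailed safety monitoring checklist of side effects and/or adverse reactions". On Days 1-10 participants are to contact the PI if they have an event on that checklist.
- **Safety Monitoring.** "Safety monitoring will include active and passive surveillance procedures using pre-existing safety monitoring guidelines". When a checklist event is reported, "study personnel will then contact the study physician". Neither the guidelines nor the checklist is reproduced.
- **Visit 2.** This is on Day 11. No visit, call or oral check is described between Day 1 and Day 11. The daily log chart is for recording doses.

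**The concern.** The protocol itself treats the mouth as a safety site. It inspects it before dosing, plans repeat inspections and makes a lesion a ground for withdrawal. The product is placed under the tongue twice a day. Yet the one printed list of events to watch for leaves the mouth out, and for the first ten days that kind of list is the only stated trigger for contact.

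A participant who develops a sore under the tongue on, say, Day 3 would then have no listed reason to call and could keep dosing onto it until Day 11. The PI/physician could not apply criterion 1 in the meantime without knowing of the lesion. What is at stake is participant safety and the timely use of a stated stopping criterion. Randomization, outcomes, type I error and power are not involved.

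**Working it through.** **1. Dose frequency, checked against the plan's own figure.** Under Investigational Product & Dosing Schedule, the active product is 2000 mg in 30 mL, given as 0.5 cc twice daily, with a stated dose of 67 mg/day.

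2000/30 mg/mL × 0.5 mL × 2 per day = 66.7 mg/day, which rounds to 67. This reproduces the stated figure and confirms two doses a day. The supply is for 15 days, so the nominal course is 15 × 2 = 30 doses.

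**2. Period without a visit.** Visit 1 is Day 1 and Visit 2 is Day 11. Days 2-10 (9 days) have no visit, and the interval between the two inspections is 11 − 1 = 10 days.

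**3. Doses taken before the next inspection.** Days 2-10 give 9 × 2 = 18 doses. The plan does not say how many doses are taken on Day 1 (0, 1 or 2), nor whether the Day 11 morning dose comes before the visit (0 or 1).

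| Doses on Day 1 | Days 1-10 | Before Visit 2 | Course to Day 15 | Share before Visit 2 |
|---|---|---|---|---|
| 0 | 18 | 18-19 | 28 | 64-68% |
| 1 | 19 | 19-20 | 29 | 66-69% |
| 2 | 20 | 20-21 | 30 | 67-70% |

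The course column is Day 1 doses plus 14 × 2 = 28. Days 1-10 therefore hold 18-20 doses, and 21 is reached only by adding the Day 11 morning dose. Against the nominal 30, 18 doses is 60%, 20 is 67% and 21 is 70%. These figures measure exposure time without a prompt, not lesion risk.

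**4. Does the list prompt a mouth report?** Mouth, oral or sublingual items on the printed list: 0 of 11.

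**5. Does the checklist match the list?** Safety Monitoring moves from checklist events to a reference to the stopping criteria, and criterion 1 then refers to the printed list. The list's heading also resembles the Visit 1 description of the checklist. A match is the natural reading, but it cannot be confirmed.

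**6. Who is re-examined at Visits 2-6?** The only stated condition for the repeat oral assessments is that the participant continues in the study, and the Visit 2 text uses similar wording for everyone. The natural reading is all continuing participants. Some doubt remains: the sentence follows the lesion-found instructions, and the procedures listed for Visits 2-6 do not name an oral assessment.

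**The case against.** The strongest objection is that the gap depends on papers that cannot be seen. The checklist and the monitoring guidelines are not reproduced, and consent pages are absent from the text reviewed. Any of them could carry a mouth prompt. This stands, and it is why the point is conditional.

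Second, a reader might infer that the stopping criterion and the list contradict each other. They do not. Criterion 1 gives lesions and side effects as alternatives, and the list serves the second. Lesions have their own detection route, direct inspection. The gap is in prompting only.

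Third, a reader might infer that lesions would go undetected throughout dosing. On the natural reading every continuing participant is inspected from Day 11, so a lesion still present then should be found. Any lesion found at Visit 1 already leads to a call to the study physician. Known allergy to CBD, coconut/sesame oil or tree nuts is an exclusion. Participants can also report unprompted or withdraw at any time. All of this stands and limits the point to a delay.

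Fourth, no harm is shown. The documents neither say that the product causes oral lesions nor give a rate. The side effects cited under CBD use come from products that were swallowed, so they say nothing about tolerability under the tongue in either direction.

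**Conclusion.** The point holds as a minor, conditional gap in safety prompting. If the participant checklist matches the printed list, a mouth lesion arising after Visit 1 has no listed reporting trigger until Visit 2. Use of criterion 1 could then be delayed by up to about 10 days, while roughly two-thirds of the doses are taken.

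This rests on two assumptions: that the unseen checklist and guidelines add no mouth item, and that oral assessments from Day 11 cover everyone. If the first fails, all that remains is a printed list that should agree with the checklist. If the second fails, participants with a clear mouth at Visit 1 would also lack inspection later. The wording does not favour that narrower reading, and the point does not rely on it. Criterion 1 is a matter of judgement in any case, so an earlier report would permit an earlier decision without dictating it.

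**What to change.** Add one item, for example *sores, ulcers, bleeding, burning or pain in the mouth or under the tongue*, to the checklist used for self-report, for reading at visits and for the 1-week follow-up call. Add the same item to the printed list under the stopping criteria. If the checklist already has such an item, only the printed list needs changing.

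**Cost.** Reading the item at 5 visits and 1 call for 30 participants is (5 + 1) × 30 = 180 readings. At an assumed 5 seconds each, that is 180 × 5 = 900 s, or 15 minutes over the whole study. A few more minor oral reports are likely. Under Safety Monitoring, each would need a call to the study physician, an entry in the participant's file and a report to the IRB within 24-48 hours.

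Separately, and as a clarification of wording only, the protocol could state that the oral assessment at Visits 2-6 applies to all participants and name it in those visits' procedures. On the natural reading this adds no examination time.

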Inclusion Criteria: a) male and female adults between the ages of 18-35 years and b) English speaking, and c) both female and male subjects must be currently practicing acceptable methods of birth control, such as abstinence, and methods of contraception (barriers, oral, patch or other prophylactic methods).

Exclusion Criteria: (a) use of cannabis products on a regular basis OR positive urine test for cannabis, (b) history of seizure disorder (self or family), traumatic brain injury, liver, kidney, or cardiovascular disease, (c) current medical condition that would prevent the participant from performing strenuous resistance exercise, (d) weight lifting for the lower extremities (legs) more than twice a week, (e) currently experiencing pain in the hips, leg, or knee region, (f) pregnancy, lactating or positive urine pregnancy test, (g) known allergy to CBD, coconut/sesame oil, or tree nuts (coconut).

If the participant self-reports that they are currently using tobacco products or a nutritional/dietary supplement, or if they take prescription anti-depressant/anxiety medications, the participant may continue to use the product(s) but they must be on a stable dose at least 3 months prior to randomization as well as during the 15-day study trial period. Also, if the participant is currently using OTC anti-inflammatory medication (e.g., Advil, Aleve, Aspirin) on a regular basis, we will ask that they stop taking the medication at least 7 days before randomization and refrain from using the product during their participation in the study trial.

Investigational Product & Dosing Schedule

Participants will be provided a 30mL bottle with a syringe dropper on day 1 with instructions to ingest the solution orally using a sublingual route of administration (0.5 cc ~1/2 dropper) twice per day (BID) 12 hours apart (morning and evening) at the prescribed daily dosages: Vehicle-control (0mg/30mL hemp extract = no hemp extract), and active Dose (2000mg/30mL hemp extract = 67mg/day). The sublingual route of administration allows the product to be absorbed directly into venous circulation, and thus bypasses the liver and eliminates the consequences of first pass metabolism; ultimately increasing its bio-availability. The bioavailability of CBD administered orally (including sublingual) is estimated to be 13-19% and its half-life estimated to be around 18-32 hours. 35,36

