Visit 2 (Pre-exercise measurements and exercise protocol, Day 11)

Participants will be assessed actively (including vital signs) at each subsequent visit by study personnel using the side effects/adverse events checklist. Each participant will be read each side effect/adverse reaction from the checklist and instructed to self-report as yes (go) or no (no go). For participants who continue in the study, the following procedures will be performed: completion of psychological questionnaires (FPQ-9, PCS, PASS-20, PSQI, & LEFS), followed by tests of muscle soreness, quantitative sensory testing (QST), the timed stair climbing test (TSCT) and isometric strength measures to evaluate leg function. Participants will then undergo a standardized single bout of eccentric resistance exercise to the dominant quadriceps muscle. An isokinetic dynamometer (Biodex System 4 Pro, Biodex Medical Systems, Inc., Shirley, NY) will be used for the eccentric exercise protocol. Each participant will then perform five sets of twenty-five repetitions. Exercise will be performed using concentric (meaning shortening of muscles during contraction) and eccentric (lengthening of the muscle while still developing tension). The angular velocity will be set at 60°/sec for concentric and 90°/sec for eccentric actions. Participants will be given a three-minute rest period between sets. Each subject will receive \$15 for completing the test session.

Visit 3, 4, & 5 (Follow-up measurements @ 24, 48, & 72-hr post-exercise, Day 12, 13, & 14)
The following procedures will be performed: completion of psychological questionnaires (PCS & LEFS), followed by tests of muscle soreness and leg function testing (TSCT and isometric strength measures). Participants will receive \$5 for completing visits 3, 4 and 5.

Visit 6 (Follow-up measurements @ 96-hr post-exercise, Day 15)

The following procedures will be performed: completion of psychological questionnaires (FPQ-9, PCS, PASS-20, PSQI, & LEFS), followed by tests of muscle soreness, QST, and leg function testing (TSCT and isometric strength measures). At the end of the session each participant will be asked if they thought they were taking the active CBD product or placebo. Participants will receive \$10 for completing visit 6.

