Participants will be informed during the consenting period, both in writing on the consent form and verbally, that participants will likely experience soreness and stiffness within the exercised muscles after completing the exercise protocol. We postulate that participants will likely experience some level of heightened fear and anxiety (pain-related or other) in the 10-day wash-in phase of the investigational test article before they undergo the experimental exercise protocol and recovery phase. We feel this will be quantifiable on the self-reported psychological questionnaires that the participants will complete before and after the experimental protocol.

Data Management & Analysis

All information and data collected will be stored in locked filing cabinets or in computers with security passwords and accessed only by members of the research team. This process facilitates

data entry and collection, allows for participants to complete self-report questionnaires, and offers optimal security for collecting research-related information. The proposed Data Management will be housed within the Human Performance Laboratory and a secure webbased platform approved by UF (e.g. Redcap) will be used.

Outcome measures will be analyzed using a two-way ANOVA with repeated measures (between-group; within-time) or distribution free test (e.g Friedmans) as indicated by data distribution. Statistical significance will be set at p<0.05. If significant interactions occur, the Tukey post-hoc test will be used to reveal where the differences occur. We will calculate effect sizes and estimates of precision for all outcomes. All data analyses will be performed using SPSS® for Windows 16.0 (SPSS, Inc., Chicago, IL).

A **Data and Safety Monitoring Plan** will consist of two components: (1) overseeing participant safety and data monitoring, and (2) performance of monitoring. Since this project is viewed as low potential risk, all key personnel will perform all data and safety monitoring on an as needed basis.

7. Possible Benefits:

There is no known direct benefit from participating in this study. Study participants have the option of being paid for their time performing research related duties or they may choose to receive extra credit for a course they are currently taking and that may or may not be considered a benefit. There are no other obvious benefits to the study participant.

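### Undefined non-compliance can end participation with no later outcome collection planned and no analysis set named, and a self-completed log is the only record of dosing

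*Combined protocol and SAP*

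**What the plan says.** Under Safety Monitoring and Stopping Criteria, item 3 of the participant stopping list reads "Lack of compliance with protocol". It has no definition, threshold or method of assessment. Item 1 of the same list begins "The PI/physician decides that the participant should be withdrawn for" safety reasons, so the list concerns people leaving the study, and it offers no option to stop product and stay in follow-up. Item 6 deals separately with missed visits and, unlike item 3, carries a definition: "lost to follow-up will be defined as a subject failing to attend planned study visits or failure to respond to contacts by study personnel" after two documented attempts.

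At Visit 2, after the side-effect checklist, the text says "For participants who continue in the study, the following procedures will be performed". No efficacy assessment after withdrawal is described. The telephone call one week after completion is for safety only.

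On dosing, the Visit 1 section says "Each participant will be provided a daily log chart to record their daily CBD doses for compliance and monitoring purposes". The Investigational Product section says "Participants will be provided a 30mL bottle with a syringe dropper on day 1", but no return, weighing or volume check follows. The urine cannabinoid test is an eligibility check: "Results of urine screening for pregnancy and toxicology (presence of cannabinoids) will be available and assessed during the first visit". No repeat is described.

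Data Management & Analysis specifies a "two-way ANOVA with repeated measures (between-group; within-time") or a distribution-free test. It names no analysis set and no rule for missing data.

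**The concern.** Compliance is observed after randomisation. If people who break the protocol leave and are not measured again, the arms compared at the end are no longer the arms that were randomised.

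The link to the outcome is plausible here. Item 3 refers to the protocol as a whole, not only to dosing. The Study Population section asks regular users of over-the-counter anti-inflammatories to refrain from them during the trial, and the Visit 1 section asks participants not to start resistance training. The sorest participants have most reason to break the first of these, and soreness is a primary outcome. If the product works, that pressure would differ by arm.

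Timing adds to the loss. The exercise bout is on Day 11, so anyone removed before then has no post-exercise soreness or LEFS score. Anyone removed on Days 12 to 14 has an incomplete record for peak and duration of soreness, and a complete-case repeated-measures ANOVA drops that person altogether. No model recovers values that were not measured, so the collection plan has to be settled before recruitment.

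The adherence question is separate. With a self-completed log as the only dosing record, a null finding could mean that the product does nothing or that it was not taken. The study is meant to supply preliminary data for a larger trial, so this ambiguity would carry forward.

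**Working it through.** The documents give no power calculation, SD, effect size or dropout allowance, so there is no stated figure to reproduce. What follows only sizes the problem.

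**Inputs from the documents.** 15 per arm (Study Location & Design); significance at 0.05, taken as two-sided (Data Management & Analysis); 0.5 mL twice daily from a 30 mL bottle (Investigational Product section).

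**Assumptions.** The number removed k, the correlation ρ between the tendency to be removed and the outcome, removal from one arm only, SD = 1, and a t-test on one outcome standing in for the repeated-measures ANOVA.

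**1. Shift in the arm mean with no true effect.** Remove the k of 15 with the highest removal score. If S_k is the sum of the k largest expected values in a standard normal sample of 15, the retained mean moves by

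shift = ρ × S_k / (15 − k).

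The four largest expected values are 1.736, 1.248, 0.948 and 0.715.

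- k = 2: S = 2.984 and 2.984/13 = 0.230. Times 0.3 gives 0.07; times 0.7 gives 0.16.
- k = 4: S = 4.646 (from unrounded values) and 4.646/11 = 0.422. Times 0.3 gives 0.13; times 0.7 gives 0.30.

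A simulation of 40,000 trials per scenario agrees and adds the type I error:

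| Removed from one arm | ρ | Shift (SD) | Type I error, retained only |
|---|---|---|---|
| 1 of 15 | 0.3 to 0.7 | 0.04 to 0.09 | 0.052 to 0.058 |
| 2 of 15 | 0.3 to 0.7 | 0.07 to 0.16 | 0.053 to 0.078 |
| 3 of 15 | 0.3 to 0.7 | 0.10 to 0.23 | 0.057 to 0.098 |
| 4 of 15 | 0.3 to 0.7 | 0.13 to 0.30 | 0.063 to 0.123 |

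Analysing all 30 as randomised gave 0.048 to 0.051 in every scenario.

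**Scale.** The standard error of the difference at 15 per arm is √(2/15) = 0.37 SD. Two removals therefore cost about 0.2 to 0.4 of a standard error (0.07/0.37 to 0.16/0.37), and four about 0.4 to 0.8.

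**Direction.** Losing the sorest people from the active arm favours CBD; losing them from the vehicle arm hides a benefit. With the same k and ρ in both arms the expected shifts are equal and their difference is zero.

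**2. Loss of precision.** For n per arm, power comes from the noncentral t with df = 2n − 2 and noncentrality d√(n/2). Solving for 80% power:

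- n = 15: df 28, critical t 2.048, d = 1.06 (noncentrality 1.06 × 2.739 = 2.90).
- n = 13: df 24, critical t 2.064, d = 1.145 (1.145 × 2.550 = 2.92).
- n = 12: d = 1.20.

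Power for an effect of 1.06 SD falls from 80% to 74% at 13 per arm and 70% at 12.

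**3. Volume check.** 0.5 mL × 2 × 15 days = 15 mL used, leaving 30 − 15 = 15 mL. The dispensed bottle is therefore large enough for a before-and-after weight to be informative.

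**The case against.** Several stronger readings are tempting, and the documents do not support them.

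- A reader might infer that removal is decided from the log. The log is provided for compliance and monitoring, but nothing ties it to item 3, whose method of judgement is unstated. The two issues are also partly opposed: a non-taker who records every dose would not be found by the log.
- A reader might infer that outcomes are never collected for those removed. Data up to removal are collected, and nothing says they are discarded. The lack of later collection is read from silence, and the Visit 2 sentence about those who continue follows the side-effect checklist, not a compliance check.
- A reader might infer that the trial becomes a comparison of compliers. How far it moves that way depends on the number removed and on an analysis set that is not named.
- A difference in taste between arms should not be offered as a mechanism. The Investigational Product section says the active and vehicle liquids cannot be told apart.

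The opposing case also notes that ten of the fifteen days come before any induced soreness, that moderate or severe product-related events already end participation under the safety rule, that the scenarios are assumed and one-sided, and that the study is exploratory. These points limit the likely size, and for one or two removals the distortion is small. They do not remove the problem: a written rule lets randomised people leave for an undefined post-randomisation reason, and the ban on anti-inflammatories bears most heavily after Day 11, when soreness is being measured.

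**Conclusion.** The concern holds in this form: non-compliance is an undefined reason to end participation, no outcome collection after withdrawal is planned, and no analysis set is named, so the comparison may drift towards compliers. Separately, dosing adherence rests on self-report alone.

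The size is conditional on assumed numbers. One or two removals from one arm matter little: for two, 0.07 to 0.16 SD, with type I error at most about 0.08. Several removals linked to soreness matter more: for four of fifteen, up to 0.30 SD and about 0.12. Balanced losses would largely cancel as bias, though precision would still suffer, with the detectable effect rising from 1.06 SD to about 1.15 SD at 13 per arm. The change is worth making because it is cheap and cannot be made after the data are lost.

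**What to change.** 1. State that non-compliance alone does not end outcome collection. Continue the scheduled soreness, LEFS and function assessments in every randomised participant who still consents. Participation in the exercise bout and any stopping for safety stay with the study physician, outside this point.
2. Name the analysis set as all randomised, analysed in the assigned arm with all available data. A mixed model for repeated measures would serve, because it keeps participants who miss a visit. Report withdrawals by arm, with reason and day.
3. Ask participants to bring the bottle, weigh it at existing visits (for example 1, 2 and 6), and report the volume removed by arm beside the log.

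Cost: a few sentences in the protocol and a scale. The as-randomised estimate will include some non-takers and may be slightly smaller. Bottle weight shows what left the bottle, not what was swallowed, so it is a more objective but imperfect measure. Anyone who does not undergo the exercise bout still has no post-injury outcome, so the earliest losses are reduced only in part. No dose or safety stopping rule changes.
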